1.1 Overview of disease pathogenesis, epidemiology, and current treatment

Lung cancer is the leading cause of cancer death in the United States. Lung and bronchial cancer are expected to account for an estimated 221,200 new cases (115,610 in men and 105,590 in women) and 158,040 deaths (86,630 in men and 71,660 in women) in 2015.¹ Only 16.8% of lung cancer patients are alive for 5 years or more after their diagnosis. Non-small cell lung carcinoma (NSCLC) accounts for over 85% of all lung cancer cases. Most patients are diagnosed with advanced or metastatic (stage IIIB/IV) disease,² and current first-line treatment options for these patients are limited. In patients with advanced NSCLC, first-line platinum-based doublet chemotherapy yields 1-year overall survival (OS) rates of only 30–40% and can cause significant toxicities that may complicate treatment.² However, much progress has recently been made in the diagnosis and treatment of lung cancer including screening methods, minimally invasive techniques for diagnosis and treatment, and advances in radiation therapy (RT), including stereotactic body RT (SBRT), targeted therapies, and immunotherapies.^{3–6}

Uveal melanoma represents approximately 85% of all ocular melanomas. Metastatic disease develops in up to 50% of patients and is associated with poor prognosis.⁷ The most frequent site of metastasis is the liver (95%), followed by the lungs (24%), bone (16%), and skin (11%).^{8,9} Median survival for patients with liver metastases is approximately 4–6 months with a 1-year survival of approximately 10–15%, whereas patients with metastases not involving the liver have a median survival of approximately 19–28 months with a 1-year survival of approximately 76%.^{10–12} There is no proven treatment for metastatic uveal melanoma, and standard therapies for cutaneous melanoma are often adopted but show limited activity.¹¹ As uveal and cutaneous melanomas exhibit marked differences in their molecular features,¹³ dedicated therapies for metastatic uveal melanoma are needed to improve the outcomes of patients with this hard-to-treat disease.

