Tumor assessments: Tumor assessments will be performed at baseline and every eight (8) weeks thereafter until completion of the protocol-specified study treatment, and 30 days after the last dose of nivolumab. Disease status will be assessed using both RECIST 1.1 and modified irRC (assessments will be performed at specified time points). Serum alanine aminotransferase (ALT) levels will be assessed on day 1 of each cycle. The ALT level must be within the acceptable range before administering the study drug combination, and dosing will be discontinued either temporarily or permanently for any patient who has a severe cytokine reaction, elevated ALT level ($> 5 \times$ upper limit of normal [ULN]), or any other Grade 4 or greater adverse effect.

[figure not shown]
5. Study design

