A screening medical history and physical exam will be performed (baseline symptom-medical history and physical examination are not required if the screening was conducted within 7 to 28 days prior to day 0 of ADV/HSV-tk). Patients presenting with any medical history, physical exam, or laboratory abnormality that, in the opinion of the treating physician, would put their safety at risk will be excluded. A window of ± 5 days is allowed for study visits and assessments (except as otherwise specified). A physical exam will be performed on days 0 and 17; every 4 weeks thereafter until completion of the protocol-specified treatment; and at end of treatment (EOT). Vital sign (blood pressure, heart rate, and oral temperature) measurements will be performed at each physical exam. A 12-lead electrocardiogram (ECG) will be performed at screening, at EOT, and when clinically indicated. Multigated acquisition (MUGA) scan or echocardiogram (ECHO) will be performed when clinically indicated. The same method (ECHO or MUGA scan) must be used throughout the duration of the study. A blood sample for complete blood count (CBC) with platelet count and differential white blood cell (WBC) count will be obtained at screening, on days 0 and 17, every 4 weeks thereafter until completion of the protocol-specified treatment, at EOT, and when clinically indicated. If a patient is found to have an absolute neutrophil count (ANC) $< 1.5 \times 10^9/L$, platelet count $< 100 \times 10^9/L$, or both, the CBC with differential should be repeated at least every other day until the ANC and platelet count have exceeded these values. A blood sample for clinical chemistry panel (glucose, albumin, sodium, potassium, carbon dioxide, chloride, blood urea nitrogen [BUN], creatinine, total bilirubin, alkaline phosphatase, aspartate transaminase [AST], and ALT) and evaluation of magnesium and lactate dehydrogenase will be obtained at screening, on days 0 and 17, every 4 weeks thereafter until completion of the protocol-specified treatment, at EOT, and when clinically indicated. Prothrombin time (PT), international normalized ratio (INR), and activated partial thromboplastin time (aPTT) testing will be performed at screening, on day 17, every 4 weeks thereafter until completion of the protocol-specified treatment, and at EOT. For women of childbearing potential (WOCBP), the results of a serum β -human chorionic gonadotropin (β -hCG) pregnancy test must be negative within 7 days of the administration of the first treatment dose. If the screening serum β -hCG pregnancy test is performed more than 7 days before ADV/HSV-tk dosing, it must be repeated at baseline, with results known to be negative prior to the administration of the first dose of the study treatment. Serum β -hCG pregnancy testing is to be repeated as clinically indicated. Laboratory tests may be done more frequently if medically indicated. Patients will be assessed for AEs and SAEs from informed consent signing up to and including 30 days after the last treatment dose. Study treatment-related AEs occurring beyond 30 days after the last dose of nivolumab and any study patient death should also be reported. Toxicity will be defined as any treatment-related death or any \geq Grade 3 toxicity excluding alopecia and constitutional symptoms as assessed by NCI CTCAE v4.03. Patients whose treatment is interrupted or permanently discontinued due to an AE including

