- Histologically or cytologically confirmed stage IV metastatic squamous or non-squamous NSCLC that has progressed after a platinum-based chemotherapy and after a single-agent immunotherapy **OR** histologically or cytologically confirmed metastatic uveal melanoma that is immunotherapy naïve.
- Evaluable or measurable disease as per RECIST 1:1, a target lesion of suitable diameter (at least 5 mm) for SBRT, and a non-target lesion of at least 1 cm in diameter for abscopal effect evaluation.
- ≥ 4 weeks since any major surgery.
- A 2-week washout period post any prior systemic anticancer therapy, RT, and/or investigational therapy is required prior to trial entry. Subject should be adequately recovered from the acute toxicities of any prior therapy.
- Life expectancy ≥ 6 months.
- ECOG performance status of 0–1.
- Adequate bone marrow function:
 - ANC $\geq 1.5 \times 10^9/L$ (without granulocyte colony stimulating factor support within 2 weeks of laboratory test used to determine eligibility)
 - Platelets $\geq 100 \times 10^9/L$ (without transfusion within 2 weeks of laboratory test used to determine eligibility)
 - Hemoglobin $\geq 8 \text{ g/dL}$ (without blood transfusion)
 - WBC count $> 2,500/\mu L$ and $< 15,000/\mu L$
 - Lymphocyte count $\geq 500/\mu L$
- Adequate liver function:
 - Serum bilirubin $\leq 1.0 \times \text{ULN}$ (patients with known Gilbert's disease who have serum bilirubin level $\leq 3 \times \text{ULN}$ may be enrolled)

- Serum transaminases (AST or ALT) activity $\leq 2.5 \times$ ULN with normal alkaline phosphatase (patients with liver metastases $\leq 5 \times$ ULN) OR AST and ALT $\leq 1.5 \times$ ULN with an alkaline phosphatase $> 2.5 \times$ ULN
- INR or PT and aPTT $\leq 1.5 \times$ ULN (unless patient is receiving anticoagulant therapy as long as PT or aPTT is within therapeutic range of intended use of anticoagulants);
- Adequate renal function: serum creatinine $< 2 \times$ ULN.
- WOCBP must have a negative serum pregnancy test within 7 days prior to the administration of the first study treatment. Women must not be lactating.
- WOCBP and men must practice an effective method of birth control (See Section 12.5).
- Signed informed consent to participate in the study must be obtained from patients after they have been fully informed of the nature and potential risks of the study by the investigator (or his/her designee) with the aid of written information.
- Willing to provide biopsies as required by the study.

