Renal Renal insufficiency and acute renal failure have been observed in patients taking Valacyclovir at the recommended dosage and/or with no previous renal conditions and may be associated with renal pain. Acyclovir, the active metabolite of Valacyclovir, is eliminated by renal clearance; therefore, the dose of Valacyclovir must be reduced in patients with renal impairment (see Dosage and administration; Patients with acute or chronic renal impairment). Geriatric patients are likely to have reduced renal function and therefore, the need for dose reduction must be considered in this group of patients. Both geriatric patients and patients with a history of renal impairment are at increased risk of developing neurological side effects and should be closely monitored for evidence of these effects. In the reported cases, these reactions were generally reversible on discontinuation of treatment. Cases of acute renal failure have been reported in patients without adequate hydration. Precipitation of acyclovir in renal tubules may occur when the solubility (2.5 mg/mL) is exceeded in the intratubular fluid. Adequate hydration should be maintained for all patients.

Adverse reactions:

Serious Adverse Drug Reactions

- Thrombotic thrombocytopenic purpura (TPP)/hemolytic-uremic syndrome (HUS)
- Acute renal failure
- Central nervous system effects

Adverse Drug Reaction Overview

The most frequent adverse reactions associated with the use of Valacyclovir are headache and nausea. Neurological side effects have also been reported in rare instances. Geriatric patients and patients with a history of renal impairment are at increased risk of developing these effects. In the reported cases, these reactions were generally reversible on discontinuation of treatment.

ENSIGN Clinical Trial Adverse Drug Reactions Because the ENSIGN clinical trial will be conducted under very specific conditions, the adverse reaction rates observed may not reflect the rates observed in practice and should not be compared to the rates in the clinical trials of another drug.

Herpes Zoster: Adverse drug reactions were not significantly different between patients receiving Valacyclovir and those receiving placebo or acyclovir in two double-blind, randomized clinical trials of treatment of herpes zoster (shingles) in immunocompetent patients. The most frequent adverse drug reactions reported in recipients of Valacyclovir are listed in Table 1.

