^jRelapsed/refractory and/or metastatic patients will be evaluated with /CT scan of the thorax, abdomen, and pelvis at screening, every eight (8) weeks thereafter until completion of the protocol-specified treatment and/or at the discretion of the treating physician, at EOT, and when clinically indicated. For patients with equivocal CT scan results, PET scan will be performed.

^kIn patients with accessible tumor, biopsies will be conducted at Visit 1, after the first dose of nivolumab (\pm 2 days), and if the patient progresses while on treatment, before the patient starts the new treatment.

Banked tumor tissue obtained as part of the patient's standard care and additional biopsies will be evaluated at a later time for assessment of Th1 response (IL-1, IL-2, IL-6, IL-12, IFN- α , and GM-CSF) and TILs before and after ADV/HSV-tk + Valacyclovir therapy.

^lBlood samples for correlative studies will be collected at screening, after the first dose of nivolumab (\pm 2 days), and at the end of Cycle 2 of nivolumab. An additional sample will be collected from patients whose disease progresses while on treatment. Blood samples will be collected into standard vacutainer tubes (3 green top tubes). Samples will be evaluated for profile of circulating suppressor and effector immunocytes and cytokines.

^mADV/HSV-tk will be injected intratumorally at 5×10^{11} viral particles in a 2-mL total volume on day 0 of the study. The study coordinator will dispense the 14-day quantity of Valacyclovir on Day 0 of the study. The patient will be instructed to take Valacyclovir (2 g) orally t.i.d. for 14 days (day 1 to day 15 of the study). NOTE: For patients with serum creatinine level between 1.6–2.0 \times ULN, valacyclovir dose will be reduced 50% (i.e., 1 g t.i.d.).

SBRT of 30 Gy (6 Gy X 5 fractions) will be administered over 2 weeks from day 2 to day 14 of the study. Nivolumab (480 mg) will be administered intravenously over 30 minutes every 4 weeks (\pm 1 day) starting on day 17 (\pm 1 day) of the study and continuing until disease progression, unacceptable toxicity, or up to 12 months in patients without disease progression.

ⁿAEs and SAEs will be captured from the time of informed consent signing up to and including 30 days after the final dose of nivolumab. Study treatment-related SAEs occurring beyond 30 days after the last dose of nivolumab and any study patient death should also be reported.

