12.4 Withdrawal of subjects from study

Subjects must be withdrawn from the trial (treatment and procedures) for the following reasons:

- Therapy will be discontinued temporarily or permanently for cytokine release syndrome.
- Therapy will be discontinued temporarily or permanently for elevated ALT ($> 5 \times$ ULN).
- Any Grade 4 or greater AE.

- Severe (Grade 3) or life-threatening (Grade 4) immune-mediated complications.
- TTP/HUS.
- Neurotoxicity (e.g., encephalopathy, seizures).
- Dose interruption that exceeds 21 days.
- Subject withdraws consent from study treatment and study procedures. A subject must be removed from the trial at his/her own request or at the request of his/her legally acceptable representative. At any time during the trial and without giving reasons, a subject may decline to participate further. The subject will not suffer any disadvantage as a result.
- Subject is lost to follow-up.
- Death.

Any subject removed from the trial will remain under medical supervision until discharge or transfer is medically acceptable. In all cases, the reason for withdrawal must be recorded in the CRF and the subject's medical records.

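### No creatinine, ALT or platelet value is scheduled while patients take valacyclovir 6 g/day (days 1-15); adding the existing panels at two SBRT visits is a cheap patient-safety improvement

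*Combined protocol and SAP*

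**What the plan says.** Section 7 (Safety Criteria), the section 11 footnotes and section 12 give the same timing for the CBC and the chemistry panel, which includes creatinine and ALT: "obtained at screening, on days 0 and 17, every 4 weeks thereafter until completion of the protocol-specified treatment, at EOT, and when clinically indicated". In the section 11 table, both rows are marked at screening, V1 (day 0), V7 (day 17), V8-V10 and EOT. They are blank at V2-V6, where SBRT is given.

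Under section 6, the vector is injected on day 0, valacyclovir 2 g t.i.d. runs from day 1 to day 15, and SBRT runs from day 2 to day 14. The section 11 footnote on administration adds: "The study coordinator will dispense the 14-day quantity of Valacyclovir on Day 0 of the study".

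Three rules turn on laboratory findings:

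- Sections 6 and 9.2 halve valacyclovir for creatinine of 1.6-2.0 × ULN. No time of measurement is attached.
- Section 4 (Tumor assessments) states: "The ALT level must be within the acceptable range before administering the study drug combination". Section 12.4 states: "Therapy will be discontinued temporarily or permanently for elevated ALT", with the threshold at 5 × ULN.
- Sections 9.2 and 12.4 take patients with TTP/HUS off treatment.

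Section 4 also times ALT to the first day of each cycle. The only cycle defined is the 4-week nivolumab cycle (Table 7), which begins on study day 17.

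**The concern.** The plan has rules for acting on renal and hepatic changes, but no scheduled measurement that could set them off while valacyclovir is being taken. The protocol itself gives reasons to want one:

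- **Renal risk.** Section 9.2 warns: "Renal insufficiency and acute renal failure have been observed in patients taking Valacyclovir at the recommended dosage and/or with no previous renal conditions". Section 8.1 admits patients with creatinine up to just under 2 × ULN.
- **Hepatic risk.** Section 9.2 reports no data at 4 g/day or more in patients with liver disease and asks for caution. Cirrhosis and hepatitis are excluded. However, section 8.1 admits patients with liver metastases and transaminases up to 5 × ULN, which is the level of the discontinuation trigger. Section 1.1 gives the liver as the commonest metastatic site in uveal melanoma (95%).
- **Vector.** Section 9.1 lists raised creatinine, liver enzymes and bilirubin, and thrombocytopenia, as possible effects.
- **Dose.** The study dose is 6 g/day for 14 days. The highest multi-day dose in Table 4 is 3 g/day (1000 mg every 8 hours).

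At stake is whether a change without symptoms can be acted on while there is still drug to reduce or stop.

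**Working it through.** No sample size, power or error rate stated in the plan bears on this point, so there is no plan figure to reproduce. The check compares dates and counts doses.

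**Step 1: scheduled draws during dosing.** Nominal days for CBC and chemistry are 0, 17, 45, 73 and 101. The number falling within days 1-15 is 0. The nominal gap between draws is 17 − 0 = 17 days, and day 17 is 17 − 15 = 2 days after dosing ends.

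**Step 2: effect of the visit window.** Sections 7 and 11 allow ±5 days, so V7 spans days 12 to 22. Applied at both ends, the gap runs from 12 − 5 = 7 days to 22 − (−5) = 27 days. A V7 draw on days 12-15 would fall within the dosing period, but nothing requires it. Nivolumab itself is held to day 17 ± 1 (sections 11 and 12).

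**Step 3: room to act on a result.** Full course: 14 days × 3 doses = 42 doses; 42 × 2 g = 84 g. Dosing days left = 15 − draw day; doses left = 3 × days left; grams left = 2 × doses left.

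| Draw day | Days left | Doses left (of 42) | Grams left (of 84) |
|---|---|---|---|
| 7 (V4 nominal) | 8 | 24 | 48 |
| 8 | 7 | 21 | 42 |
| 11 (V6 nominal) | 4 | 12 | 24 |
| 12 (V7 earliest) | 3 | 9 | 18 |
| 14 (last SBRT day) | 1 | 3 | 6 |
| 17 (V7 nominal) | 0 | 0 | 0 |

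**Step 4: what each rule has to work with.** The creatinine rule has its starting-dose input at screening or day 0. After day 1 it has no scheduled input until V7. ALT has the day-0 value and is next scheduled at V7. Platelets follow the same pattern. The every-other-day CBC repeat starts only once a low count has been found, so it does not fill the gap.

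**Step 5: cost of two added draws.** 2 × (16 + 9) = 50.

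**The case against.** The strongest reply is that the creatinine rule is a starting-dose rule. Its range matches the eligibility ceiling of 2 × ULN, and its input exists at screening and day 0. That stands. A reader might infer that the rule cannot operate at all, and the documents do not support this. What is missing is a later scheduled value, and using the rule mid-course is an addition to the plan.

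Second, the plan does not bar laboratory work during dosing. Panels may be drawn when clinically indicated, adverse events are asked about at every visit (section 13.1.1), hydration is called for (section 9.2), and the V7 window reaches back to day 12. It would therefore be wrong to say that a rise must go unseen until dosing has ended. However, tests drawn on indication depend on a symptom or a suspicion, and none of these provisions requires a value before the last dose. Section 12 mentions further schedules in a study manual. It is not among the documents, so it neither confirms nor removes the gap.

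Third, the risk context is milder than the list of warnings suggests. Section 9.2 says an earlier phase I trial used the same regimen. It links the renal and thrombocytopenic reports at 8 g/day to prolonged use in severely immunocompromised patients, and section 8.2 excludes a history of immunocompromise. Section 9.1 reports no significant vector toxicity in earlier trials. The 5 × ULN transaminase allowance is for liver metastases only. All of this lowers the expected frequency but does not supply a measurement.

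Fourth, extra draws have a price. Section 12.4 lists ALT above 5 × ULN among reasons for withdrawal, though that item allows a temporary stop. Suppose, purely as illustration, that one of the 9 uveal melanoma patients were withdrawn for a passing rise and counted as a non-responder. The chance of at least 2 responders at a 30% ORR would then fall from 80.4% to 1 − 0.7⁸ − 8 × 0.3 × 0.7⁷ = 74.5%. This is a fair reason to specify a temporary hold and a repeat test first.

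**Conclusion.** The gap is real and follows directly from the schedule: no CBC or chemistry draw is required during the 14 dosing days or at any of the five SBRT visits. The result at nominal day 17 comes when no doses are left to change. This rests on the nominal days and on the protocol as supplied, without the study manual.

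A reader might go further and infer that the run-in decision or the worst-grade toxicity tables in section 15 would be materially distorted. The documents do not support a size for that. They give no rate, onset or duration for silent renal or hepatic changes in this regimen. A change that persists to day 17 would be found there, and under section 13.1.2 an abnormality counts as an adverse event only if it is clinically significant, causes signs or symptoms, or needs therapy or a treatment change. Nor does the gap call the ORR analysis into question. The point is a cheap improvement for patient safety.

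**What to change.** Add the existing CBC and chemistry panels at two SBRT visits that patients already attend, for example V4 (nominal day 7) and V6 (nominal day 11). Mark both rows of the section 11 table and amend the matching text of sections 7 and 12. Because the ±5-day window would otherwise let the second draw slip to the last SBRT day, with about 3 doses left, fix the timing: for example, the first draw by about day 8 (21 doses left) and the second by about day 12 (9 doses left).

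State the action on each result:

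- Creatinine 1.6-2.0 × ULN: halve the remaining valacyclovir doses.
- Creatinine above 2.0 × ULN, the eligibility limit, for which the plan now gives no action: hold valacyclovir.
- ALT above 5 × ULN: apply the existing temporary or permanent discontinuation, with a temporary hold and a repeat test first for an isolated rise.

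The cost is about 50 routine draws over 25 patients, some extra laboratory adverse events, and possibly a few extra dose holds or withdrawals. No new visit, staff or assay is needed. The mid-course dose rules are new text, so the change needs a written amendment under section 16.
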